IB	Investigator's Brochure
ICF	Informed Consent Form
ICH	International Conference on Harmonization
ICMJE	International Committee of Medical Journal Editors
LMWH	Low Molecular Weight Heparin
MCP-1	Monocyte Chemoattractant Protein -1
MOP	Manual of Procedures
N	Number (typically refers to Participants)
NEJM	New England Journal of Medicine
OHRI	Ottawa Hospital Research Institute
OHSNREB	Ottawa Health Research Science Network Research Ethics Board
PAD	Peripheral Arterial Disease
PI	Principal Investigator
PTA	Percutaneous Transluminal Angioplasty
QI	Qualified Investigator
QA	Quality Assurance
QC	Quality Control
SAE	Serious Adverse Event/Serious Adverse Experience
SMC	Smooth Muscle Cells
SOP	Standard Operating Procedure
TCPs	Tri-Council Policy Statement
TLR	Target Lesion Revascularization
TNF	Tumor Necrosis Factor
TVR	Target Vessel Revascularization
UFH	Unfractionated Heparin
ULN	Upper Limit of Normal

PROTOCOL SYNOPSIS

Title:	A Phase 2, open label, pilot study to examine the use of Rivaroxaban plus Aspirin vs clopidogrel plus Aspirin for the Prevention of Restenosis after Infrainguinal Percutaneous Transluminal Angioplasty for Critical Limb Ischemia
Short Title:	The RIFLE study
Clinical Trial Phase:	Phase 2
Sponsor:	OHRI
Principal Investigator:	[name] & [name]
Indication:	Patients with Peripheral Artery Disease (PAD) requiring clopidogrel and aspirin following angioplasty
Objectives:	The aim of the trial is to measure the number of relevant clinical outcomes comparing Rivaroxaban plus Aspirin to clopidogrel plus aspirin in patients treated for CLI following PTA, to inform a large scale randomized controlled study.
Duration:	It is expected to take 12 months to enroll 40 participants. Each participant will be in the study for 12 months. The entire trial should be completed in 24 months.

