1 STUDY RATIONALE AND BACKGROUND

1.1 CRITICAL LIMB ISCHEMIA (CLI)

Peripheral arterial disease (PAD) affects over 27 million people in the industrialized world, and is associated with significant morbidity and mortality¹. Up to 10% of patients with PAD² will develop critical limb ischemia (CLI) presenting as resting pain, ulcers, gangrene, and limb loss^{1;3;4}. The typical prognosis of CLI is poor. Within 3 months of onset, 12% of patients will require an amputation and 9% will die; by one year the mortality rate is 22%². With rates surpassing those of patients with coronary artery disease (CAD), patients with CLI are also at high risk of stroke, acute coronary syndrome (ACS), and cardiovascular (CV) death^{5;6}.

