8 STATISTIC ANALYSIS

8.1 STUDY OUTCOMES

8.1.1 Primary Outcome

The primary outcome is a combined endpoint consisting of any Rintervention , Above ankle amputation and Stenosis (RAS)²at one year The 3 components of RAS are defined as follows:

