8.2 SAMPLE SIZE CALCULATION

Based on recent data published by Conte et al² we expect that during 1 year of follow up, 54% of participants will experience the primary outcome. A total sample of 40 participants was selected and is within the recommended approach for pilot studies evaluating effects when no prior information upon which to base the sample size is available. This sample size will allow us to detect an absolute 20% reduction in the main clinical outcome with a single sided alpha of 0.2 and power of 0.6 as recommended for pilots studies⁵⁹⁻⁶¹. The study will be considered successful if we can demonstrate a reduction in events in the intervention group supported by changes in biomarkers levels (biological plausibility).

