8.3 STATISTICAL ANALYSIS

All the continuous outcomes will be evaluated with the paired T-test or Wilcoxon-rank sum; proportions will be evaluated using the Fisher's exact test.

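### Section 8.2 states power of 0.6 with no named test and no allowance for deaths or losses; under the planned Fisher test it is 0.57 with complete data and about 0.49 to 0.55 with plausible attrition

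*Combined protocol and SAP*

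**What the plan says.** - Section 8.2 expects that "54% of participants will experience the primary outcome" within one year. It sets the target as being able to "detect an absolute 20% reduction in the main clinical outcome with a single sided alpha of 0.2 and power of 0.6". It names no test or formula and mentions neither deaths nor losses. It also defends 40 as a usual size for a pilot.
- The synopsis counts the 40 at enrolment: "It is expected to take 12 months to enroll 40 participants".
- Section 8.3 says that "proportions will be evaluated using the Fisher's exact test". It names no other method for a binary outcome and no time-to-event method.
- Section 8.1.1 builds the primary composite from reintervention, "Above ankle amputation and Stenosis". Death is not a component; overall and event-free survival are secondary outcomes (8.1.2).
- Section 1.1 says of CLI in general that "by one year the mortality rate is 22" per cent.
- Section 6.4 lists loss to follow-up among the discontinuation criteria. Section 9.4 leaves remaining missing data to be coded by the statistician. No rule covers a participant who dies without a RAS event.

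**The concern.** A participant who dies or is lost before any RAS event must be either left out or counted as event-free. Leaving such participants out reduces the number analysed; counting them as event-free shrinks the expected difference. Both lower power, and section 8.2 reports neither the choice nor its effect. The printed power also does not say which test it belongs to, and the planned test is conservative at 20 per arm.

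The pilot is meant to show whether a large trial is warranted (section 3) and to support funding applications (section 11). Someone weighing an unremarkable result should know the real chance that this design had of detecting the target effect.

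**Working it through.** **Inputs.** Control rate 0.54, reduction 0.20 (so 0.34 on rivaroxaban), one-sided alpha 0.2 and N = 40, all from 8.2; Fisher's exact test from 8.3; 22% mortality from 1.1. Assumed: 1:1 allocation (20 per arm; no ratio is stated), 54% taken as the control-arm rate, and the one-sided 0.2 of 8.2 applied to the test in 8.3, which gives no sidedness.

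**Step 1: the plan's own figure.** Pooled normal approximation, mean rate 0.44, n per arm:

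Power = Φ{[0.20 − 0.8416·√(2·0.44·0.56/n)] / √[(0.54·0.46 + 0.34·0.66)/n]}

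At n = 20 this is Φ{(0.20 − 0.132)/0.154} = Φ(0.44) = 0.67. Other methods at 20 per arm: unpooled 0.68, arcsine 0.67, continuity-corrected 0.55. None gives 0.60. The pooled formula gives 0.62 at 16 per arm and 0.605 at 15.

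**Step 2: the planned test with complete data.** Sum the two binomial probabilities over every table whose one-sided Fisher p-value is at most 0.2. At 20 per arm, 0.54 vs 0.34, power is 0.569. The test's actual size here is only about 0.13, which explains the gap from 0.67. Fisher's test first reaches 0.60 at 22 per arm (0.613; 0.592 at 21).

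**Step 3: adding attrition.** Assume constant hazards, attrition independent of RAS and equal in the arms, and 54% and 34% as rates before any attrition. Yearly hazards:

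- RAS, control: −ln(0.46) = 0.777
- RAS, rivaroxaban: −ln(0.66) = 0.416
- death at 22%: −ln(0.78) = 0.248

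RAS observed before death by one year:

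- control: 0.777/1.025 × (1 − e^−1.025) = 0.486
- rivaroxaban: 0.416/0.664 × (1 − e^−0.664) = 0.304

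Dead without RAS: 15.5% and 18.2%. Evaluable: 20 × 0.845 = 16.9 and 20 × 0.818 = 16.4, about 33 of 40. The dropped column averages Fisher power over the random number evaluable in each arm. An assumed 10% other loss adds a hazard of −ln(0.90) = 0.105.

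| Scenario | Scored event-free | Dropped |
|---|---|---|
| No attrition | 0.57 | 0.57 |
| 10% mortality | 0.55 | 0.53 |
| 22% mortality | 0.52 | 0.51 |
| 22% mortality + 10% other loss | 0.50 | 0.49 |

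**Step 4: separating the causes.** The choice of test takes 0.67 to 0.57. Attrition at 22% mortality takes a further 5 to 6 points (0.569 to 0.522 or 0.506). Against the printed 0.6, the shortfall is 3 points with complete data and 8 to 9 points at 22% mortality.

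**The case against.** A reader might infer that the 0.6 presumes all 40 are assessed at one year, and so contradicts the protocol's mortality figure. The documents do not support that. Section 8.2 never says so, and the pooled formula points the other way: it gives 0.67 at 20 per arm and 0.605 at 15, so 0.6 is about what 40 enrolled less 25% would yield. At 22% mortality with deaths scored event-free, that formula still gives 0.63. An unstated allowance cannot be ruled out. It would not rescue the figure, though, because that formula is not the planned test, and Fisher's test at 15 per arm gives 0.43.

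Three further points have force.

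- **The 22% is not this trial's rate.** It describes CLI in general. Entry is open from Rutherford category 1 (4.1), which 6.3.1 defines as mild claudication, and life expectancy under 6 months is excluded (4.2). It should be read as an upper-end value.
- **Deaths may already be counted.** Section 8.2 states the 54% as a share of participants, so it may already be net of deaths. If it is, and event-free deaths are scored as non-events with the 20-point difference unchanged, mortality costs nothing and power stays at 0.57.
- **The practical consequence is limited.** This is a pilot, 40 was also justified on pilot-size grounds, and 8.2 defines success as a reduction in events supported by biomarker changes, not as a significant test.

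These points reduce the size of the attrition effect and its importance. They do not restore 0.6 under the test in 8.3.

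**Conclusion.** The point stands as a correction to a stated figure, not as a contradiction within the protocol. Under one-sided Fisher at 0.2 with 20 per arm, the design has power 0.57 at best. Loss of outcome data lowers it further: 0.51 to 0.52 at 22% mortality, and 0.49 to 0.55 across 10% to 22% mortality and 0 to 10% other loss.

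The 0.57 rests on equal allocation and on carrying the one-sided 0.2 over to 8.3. The lower figures also need constant hazards, attrition independent of RAS and equal between arms, and 54% and 34% being rates before deaths. The 10% mortality and 10% other loss are assumptions, not figures from the documents. The correction is worth making but does not threaten the trial; confidence is medium, because the source of the 54% and the method behind the 0.6 cannot be seen.

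**What to change.** Keep N = 40. In section 8.2:

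1. Replace the power of 0.6 with the power of the one-sided Fisher test: 0.57 with complete one-year data, and about 0.49 to 0.55 across 10% to 22% mortality and 0 to 10% other loss, with the assumptions stated.
2. Give the expected number with an evaluable one-year RAS outcome (about 33 of 40 if the 22% mortality applies).
3. State whether participants who die without a RAS event are scored as non-events or excluded, and whether the 54% is before or net of deaths.

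The cost is a few sentences and a less favourable power figure. No participants, visits or procedures are added.

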8.3 STATISTICAL ANALYSIS

All the continuous outcomes will be evaluated with the paired T-test or Wilcoxon-rank sum; proportions will be evaluated using the Fisher's exact test.

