Design:	This is a pilot study conducted at one center, The Ottawa Hospital. It is a Phase 2 open label randomized controlled trial. Consenting participants, meeting all eligibility criteria will be randomized, post PTA procedure, to one of two groups: Rivaroxaban 2.5 mg BID X 90 days plus ASA 81 mg daily OR Clopidogrel 75 mg daily X 90 days plus ASA 81 mg daily Participants will have study drug dispensed at Day 1 and take medication for 90 days. ASA may be continued after the study, for both groups, as per the standard of care. Visits will occur at 7 days, 30 days, 90 days, 6 months and 12 months. Participants will be followed for 12 months (\pm 14 days) in total. Adverse events will be collected for the first 90 days .
Intervention Description:	Treatment Arm 1 Rivaroxaban 2.5 mg twice daily for 90 days (rivaroxaban will be started 6 to 8 hours after the finalization of the procedure) and 325mg of ASA on day 1 then 81 mg of ASA daily for 89 days Treatment Arm 2 Clopidogrel 300mg on Day 1 (loading dose) then 75 mg daily for 89 days and 325mg of ASA on Day 1, then 81 mg of ASA daily for 89 days
Number of participants:	40

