2 HYPOTHESIS

We hypothesize that the addition of rivaroxaban to antiplatelet agents (ASA) following PTA will lead to a reduction in the rate of any/all of the following: restenosis, amputation, and/or major cardiovascular events in patients with CLI, as compared to the treatment of clopidogrel plus ASA.

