6.3.2 Blood samples

During the entire trial, a volume of approximately 40ml blood will be sampled from each participant for research purposes, in addition to standard of care blood samples: ~10ml of blood (2 x5 ml tubes) will be obtained for research purposes at Day 1, Day 7, and Day 90 for evaluation of platelet activation (including D-dimers), coagulation markers, smooth muscle activation markers (soluble CD40/44 ligands, and ERK ½) and inflammation markers.

All research blood samples will be processed and stored in a freezer at the Thrombosis Group Research Laboratory and analyzed at the conclusion of the study after enrollment has been completed.

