8.1.2 Secondary Outcomes

1. Clinical improvement defined as cumulative improvement of 2 classes of the Rutherford scale without the need for repeated TLR in surviving patients.
2. Event-free survival
3. Overall survival
4. Target lesion revascularization (TLR) between day 1 and final visit
5. Target vessel revascularization (TVR) between day 1 and final visit
6. Peri-procedure death within 30 days
7. Cumulative rate of major adverse cardiovascular events (as defined in 8.1.2.1) between day 1 and final visit
8. Cumulative rate of major bleeding (as defined in 8.1.2.2) between day 1 and day 90.
9. Cumulative rate of minor bleeding (as defined in 8.1.2.2) between day 1 and day 90
10. Biological plausibility by measuring coagulation changes and SMC proliferation markers within 7 and 90 days based on the following markers: D-dimer, soluble CD40/44 ligands, and ERK 1/2.
11. Patency rates based on the ABI index and with an ultrasound at 6 and 12 months
12. Information about feasibility of a future study:
 - a. The total number of eligible candidates identified;

- b. The percentage of eligible patients referred to our study;
- c. The percentage of eligible patients who consent to be enrolled

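### Section 8.3 names a paired t-test, which cannot compare the two randomised arms, and Section 8.2 does not require the biomarker change to differ between them, so a change shared by both arms could count as support for rivaroxaban

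*Combined protocol and SAP*

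**What the plan says.** Section 8.3 is a single sentence. For continuous outcomes it says "All the continuous outcomes will be evaluated with the paired T-test or Wilcoxon-rank sum"; proportions go to Fisher's exact test. It does not say which of the two continuous-data tests answers which question.

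The design is two parallel groups: participants "will be randomized, post PTA procedure, to one of two groups" (Synopsis, Design). The hypothesis in Section 2 is comparative, "as compared to the treatment of clopidogrel plus ASA", and concerns restenosis, amputation and cardiovascular events.

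Biomarkers are secondary outcome 10 in Section 8.1.2: "Biological plausibility by measuring coagulation changes and SMC proliferation markers within 7 and 90 days", based on "D-dimer, soluble CD40/44 ligands, and ERK 1/2". Research blood "will be obtained for research purposes at Day 1, Day 7, and Day 90" (Section 6.3.2).

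Section 8.2 gives these markers a role in the trial's conclusion: "The study will be considered successful if we can demonstrate a reduction in events in the intervention group supported by changes in biomarkers levels". It names no comparator, direction, size or alpha for the biomarker part.

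**The concern.** With no crossover or matching, the only pairs available are two measurements on the same participant. A paired t-test therefore asks whether a marker moved from Day 1 within an arm. It cannot ask whether it moved differently on rivaroxaban than on clopidogrel.

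Everyone has the angioplasty, so movement common to both arms is to be expected whatever the drug. Section 1.2 itself reports that ERK 1/2 rose after the procedure and that aspirin plus clopidogrel did not affect it. A within-arm test cannot separate such movement from a drug effect.

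The biomarker clause is one of two stated conditions for success, and it is there to show that an event reduction is biologically plausible. If a within-arm test can satisfy it, it can be met with no drug effect on the markers, provided the shared movement runs in the direction counted as favourable. The results are meant to inform whether a full trial is justified (Sections 9.3 and 11).

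**Working it through.** The plan gives no biomarker SD, expected change, alpha or power, so there is no biomarker figure to reproduce. What follows is an illustration.

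**From the documents (Section 8.2):** 40 participants; 54% expected to have the primary outcome at one year; events assessed "with a single sided alpha of 0.2 and power of 0.6".

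**Assumed:** 20 per arm (no allocation ratio is stated); two-sided 0.05 for biomarkers; one marker at one time point; normally distributed change scores; no drug effect; both arms sharing a favourable mean change of d = 0.3, 0.5 or 0.8 SD of the change score; arms independent, and biomarkers independent of events.

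**Step 1. Paired test in the rivaroxaban arm alone.** The statistic is non-central t with 19 df and non-centrality d × √20; the critical value is 2.093.

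| d | d × √20 | P(significant, favourable) |
|---|---|---|
| 0.3 | 1.342 | 0.246 |
| 0.5 | 2.236 | 0.564 |
| 0.8 | 3.578 | 0.924 |

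This is the worst case, because the clopidogrel arm is ignored.

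**Step 2. Paired tests in both arms, with support claimed when only rivaroxaban is significant.** The probability is p × (1 − p), with p from Step 1:

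- d = 0.3: 0.246 × 0.754 = 0.19
- d = 0.5: 0.564 × 0.436 = 0.25
- d = 0.8: 0.924 × 0.076 = 0.07

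The figure falls at 0.8 SD because clopidogrel is then usually significant too. A simulation of 40,000 trials at 0.5 SD gave 0.246.

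**Step 3. Between-arm test on change.** The shared change cancels, so the favourable-direction rate is 0.05 / 2 = 0.025 at every d. Simulated two-sample t-tests gave 0.026, and rank-sum tests 0.024 to 0.026.

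**Step 4. Add the event condition.** With 20 per arm and 54% in both arms, exact binomial enumeration gives P(one-sided Fisher p ≤ 0.2) = 0.133. Multiplying:

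| Biomarker rule | d = 0.3 | d = 0.5 | d = 0.8 |
|---|---|---|---|
| Rivaroxaban arm only | 0.133 × 0.246 = 0.03 | 0.133 × 0.564 = 0.08 | 0.133 × 0.924 = 0.12 |
| Only rivaroxaban significant | 0.133 × 0.19 = 0.02 | 0.133 × 0.25 = 0.03 | 0.133 × 0.07 = 0.01 |
| Between-arm | 0.133 × 0.025 = 0.003 | 0.003 | 0.003 |

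Section 8.2 does not say that the reduction must reach p ≤ 0.2. If any numerical reduction counted, its probability would be 0.437. The first row would become 0.11, 0.25 and 0.40, and the last row 0.437 × 0.025 = 0.011.

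**Step 5. Opposite direction.** If the shared change is unfavourable and direction is enforced, the paired test is significant the favourable way with probability 0.0006 at 0.3 SD and practically zero at 0.5 and 0.8 SD.

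**The case against.** The strongest reply is that the plan is comparative in spirit. The Synopsis and Section 3 set rivaroxaban against clopidogrel or dual antiplatelet therapy, and the interim report in Section 9.5.1 includes treatment comparisons. An event reduction in the intervention group is naturally read as relative to control, and a reader may carry that contrast into the biomarker clause. Section 1.2 also gives an expected pattern: anticoagulants lower D-dimer, aspirin or clopidogrel does not, and aspirin plus clopidogrel leaves ERK 1/2 unchanged. The paired t-test may be a slip, since its usual rank-based partner is the signed-rank test, whereas the rank-sum test partners the two-sample t-test.

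Most of this stands as context. It makes a between-arm reading the likely intention and supplies a direction for D-dimer. But Section 1.2 is rationale, not a decision rule, and neither Section 8.1.2 nor Section 8.2 carries it into the success criterion. An analyst who follows Section 8.3 literally can still report within-arm change as support.

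It also stands that the rivaroxaban-only figures are a worst case. Testing both arms is the more realistic misuse, and its inflation is much smaller.

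A reader might infer that Section 8.3 offers no valid between-arm test. It does: the rank-sum test is valid for independent arms. Nor is a paired test wrong as a description of change within participants.

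**Conclusion.** The point holds and should be fixed. The only t-test named for continuous outcomes cannot compare the arms, no rule requires the test that can, and Section 8.2 does not say that supporting biomarker changes must differ between arms.

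Under the stated assumptions, the no-effect pass rate of the biomarker condition rises from 0.025 to between 0.07 and 0.25 if both arms are tested, or to between 0.25 and 0.92 if the clopidogrel arm is ignored. The documents supply neither the size nor the direction of any shared change in this trial, so these figures show what the wording permits, not what will happen.

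Two stronger readings are not supported. A reader might infer that a shared biomarker change alone could make the trial a success; Section 8.2 also requires a reduction in events. A reader might infer that the primary comparison is compromised; it is a proportion tested by Fisher's exact test and is untouched. The stakes are one of two success conditions, resting on a secondary outcome, in a 40-person pilot.

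**What to change.** In Section 8.3, replace the paired t-test with wording such as:

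> Each follow-up biomarker value (Day 7, Day 90) will be compared between the randomised arms by ANCOVA adjusted for the Day 1 value, with a confidence interval. If the distribution is clearly non-normal, judged on data pooled across arms, the Wilcoxon rank-sum test on change from Day 1 will be used instead. Paired within-arm tests are descriptive only and do not count towards success.

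In Section 8.2, reword the biomarker clause to require a between-arm difference in biomarker change favouring the intervention group.

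The cost is wording only, before analysis; the samples are already planned. The downside is that the condition becomes harder to meet. With 20 per arm, a two-sample t-test on change (38 df, non-centrality d × √10, two-sided 0.05) has power 0.34 for a true between-arm difference of 0.5 SD and 0.69 for 0.8 SD. That reflects how much 40 participants can show about a drug effect on these markers.

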8.1.1.3 RE-STENOSIS

Reported in a time-to-event fashion, defined as:

- Decrease in ABI by 0.15 (or TBI drop of 0.10) or greater as compared to post-procedure value
- Duplex ultrasound demonstrating occlusion of the graft or treated vessel
- Duplex ultrasound demonstrating critical graft stenosis (Peak Systolic Velocity \geq 300 cm/s or velocity ratio \geq 3.0)
- Angiogram, MRI or CTA demonstrating occlusion of graft or of any treated vessel, or $>$ 50% stenosis in the presence of recurrent clinical symptoms

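### Restenosis is to be reported as time-to-event and two survival outcomes are listed, but section 8.3 names no method that handles censoring and no rule for deaths or losses before an event

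*Combined protocol and SAP*

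**What the plan says.** Section 8.1.1 sets the primary outcome: "The primary outcome is a combined endpoint consisting of any Rintervention", together with above-ankle amputation and stenosis, at one year. Death is not a component. Section 8.1.1.3 introduces the restenosis component with "Reported in a time-to-event fashion, defined as". Section 8.1.2 lists "Event-free survival" and "Overall survival" as secondary outcomes and defines neither.

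Section 8.3 is one sentence: "All the continuous outcomes will be evaluated with the paired T-test or Wilcoxon-rank sum; proportions will be evaluated using the Fisher's exact test". No section names a survival estimator, a survival test, a censoring rule or a competing-risk rule.

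Three other places bear on incomplete follow-up:

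- Section 1.1 says of critical limb ischemia (CLI) that "by one year the mortality rate is 22" per cent.
- Section 6.4 lists loss to follow-up among the reasons for withdrawal.
- Section 9.4 leaves the coding of data still missing after queries to the statistician.

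Only the clinical-improvement outcome is explicitly limited to surviving patients.

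**The concern.** The plan promises outcomes that it has no method to analyse. A time to restenosis or a survival time is incomplete for anyone who leaves follow-up without the event. Fisher's test needs a yes or no for every participant. A t-test or rank-sum test on follow-up times would treat a censoring time as an event time.

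The gap reaches the primary result. Death can prevent RAS from being observed and is not itself RAS, so someone must decide how a participant who dies at month 4 without RAS enters the one-year table. The trial is open label, and under section 8.2 it succeeds if events are reduced in the intervention group with supporting biomarker changes. A counting rule chosen late could be chosen with allocation known, and the observed difference depends on it.

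**Working it through.** **Inputs from the documents.** N = 40; "54% of participants will experience the primary outcome" over one year; the aim to "detect an absolute 20% reduction in the main clinical outcome", so 54% vs 34%; one-sided alpha 0.2 and power 0.6 (all section 8.2). One-year CLI mortality is 22% (section 1.1).

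**Assumptions.** 20 per arm (no allocation ratio is stated); constant, independent hazards of RAS and death; death by one year of 22% in each arm in the absence of RAS, with a range of 10% to 30%. The range is needed because Rutherford category 1 and above is admitted, and section 6.3.1 calls category 1 mild claudication, so trial mortality may be below the CLI figure.

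**1. The plan's own power.** The pooled two-proportion formula, one-sided 0.2, 20 per arm, gives 0.671. Exact one-sided Fisher, by enumerating all 21 × 21 tables, gives 0.569. Neither is the stated 0.6. That discrepancy is a separate matter; 0.569 is the baseline used here.

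**2. RAS rates under three counting rules.** Let λ = −ln(1 − p) for RAS and δ = −ln(1 − d) for death.

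- RAS observed before death: A = λ/(λ + δ) × [1 − (1 − p)(1 − d)]
- Death before RAS: B = [1 − (1 − p)(1 − d)] − A
- Scored event-free: A. Dropped: A/(1 − B). Scored as events: A + B.

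Control, d = 0.22: λ = 0.7765, δ = 0.2485, 1 − 0.46 × 0.78 = 0.6412. So A = 0.4858 and B = 0.1554; dropped is 0.4858/0.8446 = 0.5752.

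Rivaroxaban: λ = 0.4155, 1 − 0.66 × 0.78 = 0.4852. So A = 0.3036 and B = 0.1816; dropped is 0.3036/0.8184 = 0.3710.

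| Deaths per arm | Scored event-free | Dropped | Scored as events |
|---|---|---|---|
| 10% | 51.6% vs 32.4% (19.2 points) | 55.5% vs 35.3% (20.2) | 58.6% vs 40.6% (18.0) |
| 22% | 48.6% vs 30.4% (18.2) | 57.5% vs 37.1% (20.4) | 64.1% vs 48.5% (15.6) |
| 30% | 46.5% vs 29.0% (17.5) | 59.1% vs 38.5% (20.5) | 67.8% vs 53.8% (14.0) |

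At 22% the choice of rule moves the difference by 20.4 − 15.6 = 4.8 points and the control rate by 64.1 − 48.6 = 15.5 points.

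**3. Power, one-sided 0.2, 20 per arm.** The z-test and Fisher rows are exact except the dropped rule, which is simulated (8,000 trials), as is the log-rank row.

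| Test | No deaths | 22% deaths |
|---|---|---|
| Fisher, deaths event-free | 0.569 | 0.522 |
| Fisher, deaths dropped | 0.569 | 0.51 |
| Fisher, deaths as events | 0.569 | 0.45 |
| Pooled z-test, deaths event-free | 0.690 | 0.650 |
| Log-rank, deaths censored | 0.68 | 0.65 |

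Check on the log-rank row by Schoenfeld's formula: HR = ln 0.66/ln 0.46 = 0.535. Expected events without deaths are 20 × (0.54 + 0.34) = 17.6, giving Φ(√(17.6/4) × 0.625 − 0.842) = 0.68. With deaths, 20 × (0.4858 + 0.3036) = 15.8 events give 0.66. Across 10% to 30% deaths, simulated log-rank power runs from 0.67 to 0.64.

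**4. Where the power gain comes from.** Fisher's true size at a 54% rate is 0.133 against a nominal 0.2. The pooled z-test uses the same proportions as Fisher, ignores timing, has size 0.214, and matches the log-rank test in power. The gain over Fisher is therefore mainly its conservatism at 20 per arm.

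**The case against.** The strongest defence is that RAS is specified at one year and section 8.2 powers a difference in proportions, so Fisher's test matches the primary outcome as written. That stands when every participant's status at one year is known. It does not cover those who die or are lost first, nor restenosis timing or the two survival outcomes.

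Several stronger readings are tempting and are not supported:

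- A reader might infer that the plan scores deaths and losses as event-free or drops them. No section says so. The plan is silent, and scoring them as events is equally open. For overall survival, death is itself the event.
- A reader might infer that section 8.1 defines event-free and overall survival as time-to-event. It only names them; time-to-event is their ordinary meaning. Restenosis alone is explicitly so described.
- A reader might infer that scoring deaths as event-free creates a false benefit when mortality is higher on rivaroxaban. With follow-up otherwise complete, that proportion is the cumulative incidence of RAS with death as a competing event, a legitimate quantity and the one recommended below. It misleads only if deaths by arm are not shown beside it.
- A reader might infer that ignoring event timing costs power. Step 4 shows that it costs almost nothing here.

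It is also fair that 22% is a background figure for CLI, and that this is a 40-participant pilot meant to inform a larger trial. Both limit the severity. Neither supplies the missing rule.

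**Conclusion.** The point holds in this form: one component of the primary outcome is to be reported as time-to-event, two survival outcomes are listed, the only named tests cannot handle censoring, and no section says how deaths or losses before an event are counted. Under the stated assumptions, 22% mortality lets the reported RAS difference range from 15.6 to 20.4 points according to the rule chosen. Planned-test power is 0.57 without deaths and 0.45 to 0.52 with them, against a stated 0.6.

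These figures rest on 1:1 allocation, constant independent hazards and equal mortality in the arms; at 10% mortality the spread between rules shrinks to 18.0 to 20.2 points. The absence of a method and a rule rests on no assumption. It should be fixed before the data are analysed. It does not make a Fisher comparison of RAS at one year invalid when follow-up is complete.

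**What to change.** Amend section 8.3 as follows:

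- Analyse time from randomization to first RAS, event-free survival and overall survival with the log-rank test (RAS at the one-sided 0.2 of section 8.2), each with a hazard ratio and confidence interval. State which events end event-free survival.
- Use Kaplan-Meier estimates for the two survival outcomes.
- Censor losses at the last scan or contact.
- Report one-year RAS as cumulative incidence with death before RAS as a competing event, and show deaths by arm beside it. State that this differs from the log-rank comparison, which is cause-specific, and that the two can disagree if mortality differs between arms.
- Keep Fisher's test for 30-day death and for bleeding to day 90, where follow-up is short.

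The cost is wording only: no further participants, visits or types of data. One small downside is that scan-detected restenosis dates cluster at day 30, month 6 and month 12. Simulated with detection at those visits only, log-rank power was still about 0.64 to 0.65.
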